3.3.4.1 Discontinuation of trial treatment

An individual patient will discontinue trial treatment if:

- The patient wants to discontinue trial treatment, without the need to justify the decision.
- The patient has repeatedly shown to be non-compliant with important trial procedures and, in the opinion of both, the investigator and sponsor representative, is not willing or able to adhere to the trial requirements in the future.
- The patient needs to take rescue therapy, see Section 4.2.2.1.
- The patient can no longer receive trial treatment for medical reasons (such as surgery, adverse events, other diseases, or pregnancy).

Even if the trial treatment is discontinued, the patient remains in the trial and, given his/her agreement, ideally should follow the visits and procedures outlined in the [Flow Chart](#), including the EOT and EOS visits.

If the patient is not willing to follow the whole visit schedule, at least the EOT should be conducted either immediately or as soon as possible followed by the EOS visit 16 weeks after the EOT visit.

The trial treatment discontinuation criteria apply from Week 24 onwards and require assessment and confirmation at 2 consecutive visits (discontinuation itself will apply at the second visit in the sequence)

- No reduction in pustulation severity compared to baseline

AND

- No reduction in PPP ASI of ≥ 5 points compared to baseline

A patient who meets the trial treatment discontinuation criteria may be discontinued from the trial treatment and administered rescue therapy as judged by the investigator.

The earliest trial treatment discontinuation timepoint according to this rule is at Week 28.

For individual stopping rules related to specific adverse events, please see [Section 4.2.1](#) (Other treatments and emergency procedures).

3.3.4.2 Withdrawal of consent to trial participation

Patients may withdraw their consent to trial participation at any time without the need to justify the decision.

If a patient wants to withdraw consent, the investigator should be involved in the discussion with the patient and explain the difference between trial treatment discontinuation and withdrawal of consent to trial participation, as well as explain the options for continued follow-up after trial treatment discontinuation, please see [Section 3.3.4.1](#) above.

3.3.4.3 Discontinuation of the trial by the sponsor

Boehringer Ingelheim reserves the right to discontinue the trial overall or at a particular trial site at any time for the following reasons:

1. Failure to meet expected enrolment goals overall or at a particular trial site
2. Emergence of any efficacy/safety information invalidating the earlier positive benefit-risk-assessment that could significantly affect the continuation of the trial.
3. Deviations from GCP, the trial protocol, or the contract impairing the appropriate conduct of the trial.
4. Termination of the development of the compound in this indication.

The investigator / the trial site will be reimbursed for reasonable expenses incurred in case of trial termination (except in case of the third reason).

4. TREATMENTS

4.1 INVESTIGATIONAL TREATMENTS

The investigational product has been manufactured by BI Pharma GmbH & Co. KG, Biberach, Germany. The BI 655130 molecule is an anti-human IL-36 receptor monoclonal antibody heterodimer with a molecular weight of approximately 146 kDa.

4.1.1 Identity of the Investigational Medicinal Products

The investigational product (test product and matching placebo) is provided in prefilled syringes of 1 mL volume.

Table 4.1.1: 1 Test product **BI 655130**

Substance:	BI 655130
Pharmaceutical formulation:	Solution for injection
Source:	Boehringer Ingelheim Pharma GmbH & Co. KG
Chemical form:	Anti-human IL-36 Receptor mAb
Molecular weight:	146 kDa
Unit strength:	BI 655130 [REDACTED]
Posology:	[REDACTED]
Mode of administration:	Subcutaneous injections

Table 4.1.1: 2 Test product **Placebo to BI 655130**

Substance:	Placebo to BI 655130
Pharmaceutical formulation:	Solution for injection
Source:	Boehringer Ingelheim Pharma GmbH & Co. KG
Chemical form:	Not applicable
Molecular weight:	Not applicable
Unit strength:	Not applicable
Posology:	[REDACTED]
Method and route of administration:	Subcutaneous injections

4.1.2 Selection of doses in the trial and dose modifications

The aim of the trial 1368-0016 is to select dose regimens for a confirmatory phase III trial using a MCPMod based dose finding approach.

The BI 655130 subcutaneous dose regimens in 1368-0016 are selected to represent one subcutaneous dose in the range of the optimal i.v. dose identified in PoCC trial 1368.15, two

lower effective doses (different loading and different maintenance doses) and one dose with suboptimal efficacy for the Week 16 primary analysis. Additionally, the loading dose is selected to maximize the treatment response, the duration of response, and to bring the effect earlier to steady state.

Exposure response modelling was conducted on data from 1368.15 to support dose regimen selection in 1368-0016. Specifically, a graphical analysis of the average pustule severity (subcomponent of PPP ASI) suggested an increasing dose-exposure-response relationship in a severe subgroup of PPP patients in 1368.15 (presenting with a baseline PPP ASI > 16.7). A longitudinal PK/PD model linking plasma concentration to pustule severity was developed in this subgroup to describe the observed dose-exposure-response relationship and to predict the response to various subcutaneous dosing regimens.

The highest dose regimen [REDACTED] chosen because it is the highest dose and frequency that can be conveniently administered subcutaneously without imposing undue burden on PPP patients. This regimen with a loading dose allows to maximize the dose, exposure and pustule severity response that can be obtained following extravascular administration of BI 655130. A loading dose may also allow for an earlier onset of response while also theoretically reducing the high inflammatory burden associated in patients with PPP.

The second dosing regimen [REDACTED] was chosen because a high loading dose along with a more convenient, lower maintenance subcutaneous regimen should also be therapeutic, and with an effect which is similar to that of the highest dose regimen over 16 weeks.

The third dosing regimen [REDACTED] was chosen because a lower loading dose alongside the highest proposed maintenance dose, as well as being therapeutic, should have an effect over 16 weeks which is similar to but less than the effects of the two selected highest dosing regimens.

The lowest dose selected [REDACTED] is considered to be a clinically subtherapeutic dose but is still expected to provide some relief in terms of reducing the average severity of pustules. For endpoints other than pustule severity (such as PPP ASI or pain VAS), this dose may not provide significant clinical benefit based on data from 1368.15.

A longitudinal PK/PD model was also developed to describe the % change in PPP ASI at Week 16 (primary endpoint of this trial). Although the pustule severity model is used as the primary model for dose selection, the PPP ASI model supplemented the selection of the 4 dosing regimens for 1368-0016. The predicted % change in PPP ASI at Week 16 is expected to show more separation between the 4 dose groups identified, albeit with lower overall drug effects compared to the pustule severity subcomponent.

The pharmacokinetic profiles for the regimens selected are also expected to have a wide exposure range over the span of the trial duration. It is expected with the proposed 4 doses that the PK and PD data obtained over the entire 52 weeks duration may provide a robust characterisation of the exposure-response relationship.

4.1.3 Method of assigning patients to treatment groups

After the assessment of all in- and exclusion criteria, each eligible patient will be randomised to blinded treatment arms according to a randomisation plan in a 2:1:1:1:2 ratio at Visit 2 via Interactive Response Technology (IRT). This randomisation will be stratified according to region (i.e. Japan vs non-Japan).

Note that the medication number is different from the patient number (the latter is generated during screening via the IRT system). Each syringe will have an individual medication number for dispensation.

4.1.4 Drug assignment and administration of doses for each patient

Study drugs will be administered subcutaneously. Injections will be given in a double blind fashion.

At randomisation as well as at subsequent medication dispensation visits, IRT will assign medication numbers. Site personnel will enter the medication numbers in the eCRF.

BI 655130 will be administered as a subcutaneous injection by the investigator or authorized study personnel. The date and time of the administration will be recorded in the eCRF. Details are described in the drug administration manual located in ISF.

[figure not shown]
The injection sites should avoid sites of psoriasis involvement as well as sites where the skin is tender, bruised, erythematous, or indurated, and should be alternated to other areas for subsequent doses.

4.1.5 Blinding and procedures for unblinding

4.1.5.1 Blinding

Patients and investigators involved in the trial conduct will remain blinded with regard to the randomised treatment assignments until after database lock for the final trial analysis.

To maintain the treatment blind during the trial, all patients will receive 4 injections at all dosing visits in the every 4 weeks schedule, as indicated in the [Flow Chart](#).

The primary analysis of the trial will be performed once all randomised patients have completed through 16 weeks of trial treatment. At this time, a database lock for the primary analysis will be done and treatment will be unblinded. In order to confirm the integrity of the treatment blind while the trial continues through to completion, a logistics plan will be developed to describe the mechanisms that are to be put in place to assure that the patients and investigators remain blinded to both individual patient data, as well to the primary analysis results. The blind status of trial and project team members at this time will also be clarified. The logistics plan will be finalized prior to the treatment unblind for the primary analysis.

The access to the randomisation code will be kept restricted until its release at the time of the final trial analysis once all patients have completed the trial.

A fully independent DMC will perform an un-blinded safety and efficacy assessment at specified intervals in order to ensure that patients are protected from potential harm, please refer to [Section 8.7](#) for further details.

4.1.5.2 Unblinding and breaking the code

Emergency unblinding will be available to the investigator via IRT. It must only be used in an emergency situation when the identity of the trial drug must be known to the investigator in order to provide appropriate medical treatment or otherwise assure safety of trial participants. The reason for unblinding must be documented in the source documents and/or appropriate CRF page.

Due to the requirements to report Suspected Unexpected Serious Adverse Reactions (SUSARs), it may be necessary for a representative from BI's Pharmacovigilance (PV) group to access the randomisation code for individual patients during trial conduct. The access to the code will only be given to authorised Pharmacovigilance representatives for processing in the PV database system and not be shared further.

4.1.6 Packaging, labelling, and re-supply

The investigational medicinal products will be provided by BI or a designated CRO. They will be packaged and labelled in accordance with the principles of Good Manufacturing Practice (GMP). Re-supply to the sites will be managed via an IRT system, which will also monitor expiry dates of supplies available at the sites.

For details of packaging and the description of the label, refer to the ISF.

4.1.7 Storage conditions

Drug supplies will be kept in their original packaging and in a secure limited access storage area according to the recommended storage conditions on the medication label. A temperature log must be maintained for documentation.

If the storage conditions are found to be outside the specified range, the Clinical Trial Manager (as provided in the list of contacts) must be contacted immediately.

4.1.8 Drug accountability

The investigator or designee will receive the investigational drugs delivered by the sponsor when the following requirements are fulfilled:

- Approval of the clinical trial protocol by the IRB / ethics committee
- Availability of a signed and dated clinical trial contract between the sponsor and the investigational site,
- Approval/notification of the regulatory authority, e.g. competent authority,
- Availability of the curriculum vitae of the Principal Investigator,
- Availability of a signed and dated clinical trial protocol,
- Availability of the proof of a medical license for the Principal Investigator (if applicable),
- Availability of FDA Form 1572 (if applicable).

Investigational drugs are not allowed to be used outside the context of this protocol. They must not be forwarded to other investigators or clinics.

The investigator or designee must maintain records of the product's delivery to the trial site, the inventory at the site, the use by each patient, and the return to the sponsor or warehouse / drug distribution centre or alternative disposal of unused products. If applicable, the sponsor or warehouse / drug distribution centre will maintain records of the disposal.

These records will include dates, quantities, batch / serial numbers, expiry ('use-by') dates, and the unique code numbers assigned to the investigational medicinal product and trial patients. The investigator or designee will maintain records that document adequately that the patients were provided the doses specified by the Clinical Trial Protocol (CTP) and reconcile all investigational medicinal products received from the sponsor. At the time of return to the sponsor <and/or> appointed CRO, the investigator or designee must verify that all unused or partially used drug supplies and that no remaining supplies are in the investigator's possession.

4.2 OTHER TREATMENTS, EMERGENCY PROCEDURES, RESTRICTIONS

4.2.1 Other treatments and emergency procedures

Systemic hypersensitivity including anaphylactic reaction

In case of systemic hypersensitivity including anaphylactic reaction emerging during or after injection(s) of trial medication, the investigator should consider in accordance with severity of the reaction and local standard of care to

- Stop further injection(s)

- Treat with systemic anti-histamines, i.v. steroids, and in case of a severe allergic reaction (e.g., anaphylactic reaction) epinephrine

Also draw a plasma sample for IgE and ADA as detailed in the laboratory manual (ISF) and consider the evaluation of histamine, serum tryptase, and complement components.

In case of systemic hypersensitivity, based on patient's clinical course and medical judgment, injections may be cautiously re-initiated or continued in case of mild or moderate systemic hypersensitivity (according to RCTC grading, provided in the ISF).

In case of anaphylactic reaction based on the criteria discussed in the statement paper from Sampson HA ([Appendix 10.2, R11-4890](#)) suspected to be caused by the trial medication, the investigator should discontinue treatment with study drug.

When a non-acute hypersensitivity reaction related to immune complexes (i.e., serum sickness) is suspected, please draw a sample for the laboratory assessment for circulating immune complexes.

Severe infections (according to RCTC grading in [Appendix 10.3](#)), serious infections, opportunistic or mycobacterium tuberculosis infection

Treatment of the infection should be initiated promptly according to local standard of care. No further trial medication should be administered until the active infection has resolved. Treatment with study drug may be restarted when the patient has recovered according to investigator's assessment.

Malignancies

In case of occurrence of malignant neoplasm other than appropriately treated basal cell carcinoma or squamous cell carcinoma of the skin or in situ carcinoma of uterine cervix, the investigator should discontinue treatment with study drug. Diagnostics and treatment have to be initiated according to local standard of care.

4.2.2 Restrictions

4.2.2.1 Restrictions regarding concomitant treatment

This section provides information on restrictions regarding concomitant treatment before randomisation and during the trial (after randomisation), including a definition on rescue therapy for the treatment of worsening of PPP.

Restrictions regarding concomitant treatment before randomisation

The medications (or classes of medications) listed in Table 4.2.2.1: 1 must not be taken for the time periods as specified for washout.

Table 4.2.2.1: 1 Restricted Medications before randomisation

Medication or class of medications	Restriction duration
IL36R inhibitors other than the study drug	not allowed

Table 4.2.2.1: 1 (cont.) Restricted Medications before randomisation

Medication or class of medications	Restriction duration
Biologic treatment , e.g. Secukinumab (Cosentyx®), ustekinumab (Stelara®), guselkumab (Tremfya®), ixekizumab, tildrakizumab, brodalumab Adalimumab, infliximab Natalizumab or agents that deplete B or T cells (e.g. rituximab, alemtuzumab or visilizumab)	12 weeks or 5 half-lives, whichever is greater, prior to randomisation
Investigational products for psoriasis	12 weeks or 5 half-lives, whichever is greater, prior to randomisation
Etanercept Live virus vaccinations ³	6 weeks prior to randomisation
Other systemic immunomodulating treatments (e.g. corticosteroids ¹ , methotrexate, fumaric acid esters, acitretin, ciclosporin, apremilast) Any investigational device or product (excludes psoriasis products)	4 weeks prior to randomisation
Phototherapy (e.g., UVA, UVB), topical treatment for psoriasis or any other skin condition affecting palms/soles (e.g. corticosteroids ² , vitamin D analogues, salicylic acid, tar, anthralin)	14 days prior to randomisation
Anakinra	7 days prior to randomisation

¹ There is no restriction on corticosteroids with only a topical effect (e.g. inhaled corticosteroids to treat asthma or corticosteroids drops administered in the eye or ear).

² Exception: topical steroids for use on the face, axilla, and/or genitalia with a restriction of use within 24 hours prior to trial visit in which PPP ASI is assessed.

³ Live virus vaccination should be restricted until the end of the trial.

In the event a patient with prior use of biologic treatment, systemic steroids or immunomodulating treatments is enrolled, past medical records are required to document when these treatments were stopped. All concomitant or rescue therapies will be recorded (including time of intake and dose on study days) on the appropriate pages of the CRF.

Restrictions regarding concomitant treatment during the trial

Topical treatment

Topical treatment for PPP is not allowed throughout the study. Topical treatment for other conditions is not restricted, however, the patient should avoid applying it with bare hands (e.g. use gloves) when the topical treatment is applied on affected body areas.

Topical corticosteroids

Topical corticosteroids for the treatment of PPP are not allowed during the trial unless they are needed as rescue therapy. Topical corticosteroids for body area other than palms and soles are allowed. The dose and mode of administration should be kept unchanged, if possible. The patient should avoid applying it with bare hands (e.g. use gloves).

Systemic immunomodulating treatments

Systemic corticosteroids and other immunomodulating agents (such as methotrexate, fumaric acid acitretin, ciclosporin, apremilast) for the treatment of PPP are not allowed unless they are needed as rescue therapy.

Biologic treatment

Biologic treatment is not allowed throughout the study, unless it is needed as rescue therapy.

Non-steroidal anti-inflammatory drugs (NSAIDs)

The use of NSAIDs is allowed, however it is recommended that a stable dose is maintained and the drug is not changed throughout the study up to at least the primary endpoint at Week 16.

Rescue therapy for the treatment of worsening of PPP

Rescue therapy is defined as both the use of medication such as topical corticosteroids or other topical treatment applied on the palms and/or soles, systemic immunomodulating treatments or biologics and therapy such as tonsillectomy, for the treatment of worsening of PPP.

The use of the rescue therapy leads to the discontinuation of the trial treatment, but the patient should remain in the trial observation.

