7. STATISTICAL METHODS AND DETERMINATION OF SAMPLE SIZE

This trial is designed as a randomised, parallel-group, double-blind, and placebo-controlled trial with 4 active doses of BI 655130 in patients with moderate to severe Palmoplantar Pustulosis.

The purpose of this trial is to demonstrate proof of concept of clinical activity of BI 655130 on the primary endpoint of % PPP ASI change at Week 16. For the proof of concept a combined criterion of MCPMod testing (with respect to achieving a non-flat dose response curve) and evaluation of a minimum relevant benefit is implemented. In detail, for PoC, at first a statistically significant non-flat dose-response needs to be detected. For this purpose, a multiple comparison procedure with modelling techniques (MCPMod) approach is applied. Subsequently, at least one dose should show a benefit of at least 20% compared to placebo (i.e. the maximum benefit of BI 655130 for achieving the primary endpoint, based on modelled dose-response curve using model averaging across the statistically significant models (see [Section 7.2.2](#)), shows a $\geq 20\%$ larger reduction compared to placebo).

Overall this approach is applied to define suitable dose regimens for BI 655130 regarding efficacy and safety for further pivotal testing in a subsequent study. Further assessment on the efficacy of BI 655130 at time-points after Week 16 will be performed in an exploratory manner.

Baseline refers to the measurement recorded at randomisation (Visit 2); if data at Visit 2 is missing, then data from Visit 1 will be considered baseline. The percent change from baseline of the PPP ASI score, at all follow-up visits (X), is calculated as:

$$\% \text{ PPP ASI change from baseline} = \frac{(\text{PPP ASI at Visit X} - \text{PPP ASI at baseline})}{\text{PPP ASI at baseline}} * 100.$$

For the derivation of the primary endpoint, all measurements collected after treatment discontinuation, or after the use of rescue therapy for the purpose of disease worsening, will be censored. The primary endpoint is then evaluated based on the results of a mixed effect model for repeated measurements (MMRM) which assumes that missing data up to Week 16 are handled via a missing at random approach. The estimated dose effects at Week 16 will then be analysed using the MCPMod approach techniques [[R10-1424](#), [R15-1961](#)].

Randomisation will be stratified, and analysis will be performed, based on a stratification according to Japan versus non-Japan.

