5. ENDPOINTS

5.1 PRIMARY ENDPOINT(S)

The % change in PPP ASI at Week 16 from baseline is the primary endpoint of efficacy in this trial.

Derivation of % change in PPP ASI is described in [Section 9.1.1](#).

Any data collected after use of any rescue therapy or after 6 weeks following last drug administration if a patient discontinued treatment early (to allow for incorporation of the continuing maximum treatment effect period) are censored for the purpose of the primary estimand (EC).

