C1.03b	Patient skipped an intermediate dose at or after Week 16 due to COVID 19 (all injections at one planned visit) LABEL: Patient skipped an intermediate dose at or after Week 16 due to COVID 19.	Patient missing a dose at an intermediate visit when dose at a later scheduled visit has been taken due to COVID 19.	None	#

Table 6.2: 1 (cont'd) Important protocol deviations

Category / Code	Description	Comments	Excluded from ¹	
C2	Incorrect Dosing			
C2.01	Incorrect medication received prior to Week 16 LABEL: Incorrect dose received prior to Week 16	Randomized patient who didn't receive correct planned total dose at any scheduled visit prior to Week 16. Can only be finally judged after DBL since unblinding information is required	PPS	
C2.02	Incorrect medication received at or after Week 16 LABEL: Incorrect dose received at or after Week 16	Randomized patient who didn't receive correct planned total dose at any scheduled visit at or after Week 16 Can only be finally judged after DBL since unblinding information is required	None	
C3	Randomization not followed			
C3.01	Treated without randomisation LABEL: Treated without randomisation.	Patient treated according to eCRF, but not randomised according to IVRS.	All	
C3.02	Randomization order not followed LABEL: Stratification error	Stratification error Programming check and also manual review after DBL	None	#
C4	Medication code broken			
C4.01	Medication code broken before week 16 without just cause LABEL: Code broken early without just cause.	Medication code was broken prior to DBL for the week 16 analysis for no valid reason. Final decision at the DBL meeting for the Week 16 analysis based on medical judgment.	PPS	#

Table 6.2: 1 (cont'd) Important protocol deviations

Category / Code	Description	Comments	Excluded from ¹	
C4.02	Medication code broken after week 16 without just cause	Medication code was broken after DBL for the week 16 analysis for no valid reason.	None	#
	LABEL: Code broken late without just cause.	Final decision at final DBL based on medical judgment.		
D	Concomitant medication			
D1	Previous medication			
D1.01	Washout of previous medication too short		PPS	#
	LABEL: Washout too short.			
D2	Prohibited medication use			
D2.01a	Use of restricted medication as per CTP Table 4.2.2.1: 1 on or after Screening or during the on-treatment period - when not provided as a rescue therapy to treat a worsening disease condition – prior to Week 16 primary analysis for other reason		PPS	#

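### Rescue therapy is defined by worsening of PPP but used and censored under other wordings, so the primary estimand keeps PPP ASI values after a listed treatment given for PPP that is not worse

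*Protocol*

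**What the plan says.** **What counts as rescue.** Protocol 4.2.2.1 lists topical treatment on palms or soles, "systemic immunomodulating treatments or biologics and therapy such as tonsillectomy, for the treatment of worsening of PPP". The purpose is part of the definition. The same section makes rescue a reason to stop trial treatment.

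**A second use of the term.** Protocol 3.3.4.1 sets a non-response rule from Week 24, confirmed at two consecutive visits: no reduction in pustulation severity and no PPP ASI reduction of at least 5 points. Then: "A patient who meets the trial treatment discontinuation criteria may be discontinued from the trial treatment and administered rescue therapy as judged by the investigator". It adds: "The earliest trial treatment discontinuation timepoint according to this rule is at Week 28".

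**What triggers censoring.** SAP 5.1 says "Any data collected after use of any rescue therapy", and Protocol 2.1.2 and 2.1.3 and SAP 5.2.2 agree. Protocol 7 is narrower: measurements "after the use of rescue therapy for the purpose of disease worsening, will be censored". The rule for imputing missing binary outcomes (NRI) differs in the same way. Protocol 7.3 refers to rescue for worsening, SAP 6.6.2 to any rescue treatment.

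**Use for another reason.** SAP Table 6.2: 1 codes D2.01a/b and D2.02a/b cover restricted medication "when not provided as a rescue therapy to treat a worsening disease condition". Before Week 16 (D2.01a/b) this excludes the patient from the per-protocol set (PPS). It is not an EC censoring event. SAP 6.3 also defines EC-EP, which additionally censors after restricted therapy given for other purposes. For the primary endpoint it is footnoted as a sensitivity or subgroup analysis.

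**The concern.** Protocol 2.1.1 says the primary comparison should exclude the effect of rescue therapy. If rescue depends on the recorded reason, two patients who apply the same corticosteroid to their soles in Week 10 can be handled differently. The one labelled as worsening is censored. The one labelled as persistent but not worse stays in the Week 16 analysis with a score that reflects the added treatment.

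If such use were more common on placebo, the kept values would improve the placebo mean. That would reduce the difference tested by MCPMod and compared with the 20% benefit criterion. Sites also face two passages that use the term rescue differently, and rescue has a consequence for trial treatment, so the passages must be reconciled.

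**Working it through.** **Step 1. The wording side by side.**

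| Place | What makes it rescue, or triggers the rule |
|---|---|
| Protocol 4.2.2.1 | listed type and given for worsening |
| Protocol 3.3.4.1 | permitted after confirmed non-response |
| Protocol 2.1.2, 2.1.3; SAP 5.1, 5.2.2 | any rescue therapy |
| Protocol 7 | rescue for worsening |
| NRI: Protocol 7.3 / SAP 6.6.2 | rescue for worsening / any rescue |
| SAP D2.01a/b, D2.02a/b | restricted medication that is not rescue for worsening |

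A patient who meets the 3.3.4.1 criteria may be unchanged or slightly better, and so outside the 4.2.2.1 definition. Section 3.3.4.1 is a permission inside a discontinuation rule. It is not a second definition.

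**Step 2. Can the lack-of-response route reach Week 16?** No. It opens at Week 28, and 28 − 16 = 12 weeks after the endpoint. By then no arm is on placebo: SAP 6.3 gives placebo to Arm 5 only before Week 16, and SAP 6.1 then groups Arm 5 with Arms 1 and 3.

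**Step 3. What can it reach later?** Suppose treatment stops at visit week v. Visits are four-weekly, so the next is v + 4. EC cuts data 6 weeks after the last dose.
- Last dose at the previous visit: cut-off (v − 4) + 6 = v + 2, before v + 4. No scheduled visit is exposed.
- Last dose at the stopping visit: cut-off v + 6, after v + 4. One visit is exposed.

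From Week 28 on, the SAP's Week 52 MMRM uses Weeks 28, 40 and 52. The exposed visit is in that model only if v + 4 = 40 or 52, that is v = 36 or 48. This uses planned days and assumes the treatment is not itself counted as rescue.

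**Step 4. What remains before Week 16?** Take a listed treatment given in Week 10 for PPP that is not worse. Under 4.2.2.1 it is not rescue, so EC does not censor it. The stop of trial treatment tied to rescue need not follow, so the 6-week cut-off need not start. The Week 16 value stays in EC, and D2.01a/b removes the patient from the PPS only. Whether EC-EP censors it depends on what restricted therapy means there, and no list is named. The D2 codes point to Protocol Table 4.2.2.1: 1, which is headed as applying before randomisation and omits tonsillectomy, although the rescue definition includes it.

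**Step 5. Size.** Inputs from Protocol 7.5: placebo mean −25%, maximum difference 30 points, SD 35%, allocation 40/20/20/20/40. As a check on the tool, the linear 30-point scenario was simulated (10,000 trials). Relative doses 0/0.50/0.64/0.86/1 were recovered from the SAP linear contrast because the doses are redacted. Candidate models were grid-fitted and averaged with weights exp(−0.5·AIC).

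- Threshold 25: 75.6%, against 77.1% stated.
- Threshold 20: 92.3%, against 93.2% stated.

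Of 14 table entries tested, 13 came within 2 points. The exponential scenario at threshold 25 did not (75.3% against 79.0%). That is put down to the approximate fitting and redacted doses, not to an error in the plan.

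Now let a share f of placebo patients use such treatment and gain x further points that EC keeps. The placebo mean improves by f·x and the difference becomes 30 − f·x. Both f and x are assumptions.

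| f | x | f·x | Difference | Success, threshold 25 | Success, threshold 20 |
|---|---|---|---|---|---|
| 0 | – | 0 | 30 | 75.6% | 92.3% |
| 5% | 10 | 0.5 | 29.5 | 73.9% | 91.5% |
| 5% | 20 | 1.0 | 29.0 | 71.3% | 90.3% |
| 10% | 10 | 1.0 | 29.0 | 72.3% | 90.9% |
| 10% | 20 | 2.0 | 28.0 | 66.4% | 87.5% |

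The two rows with f·x = 1.0 differ only by simulation error. No use in the active arms is assumed; such use would push the other way.

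**The case against.** The strongest reply is that the plan already covers this. Treating PPP with these agents outside rescue is prohibited by Protocol 4.2.2.1. Such use before Week 16 is an important deviation with PPS exclusion, and EC-EP is pre-specified. Discrepant data are reviewed before database lock, and preferring EC-EP as primary is a choice between estimands. Much of this stands: the matter is a choice in the primary estimand with planned sensitivity analyses, not an unaddressed gap. But the proof-of-concept decision rests on the primary analysis, and EC-EP does not identify its own list.

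A second reply is that 3.3.4.1 itself calls the treatment rescue therapy, so the any-rescue trigger in the SAP would censor it. That is the natural reading of SAP 5.1. It does not settle Protocol 7 or 7.3, and it does nothing for pre-Week-16 use that no passage calls rescue.

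Third, bias from placebo use works against the drug, and use in active arms would offset it. Both are correct.

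Fourth, SAP 7.6.3 on rescue use is cited but absent from the published text, so operational detail may exist there. This also stands.

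**Conclusion.** The inconsistency is real and worth removing. At Week 16 it has one consequence: EC keeps PPP ASI values measured after a listed treatment given for PPP that is not labelled as worsening. The documents give no rate of such use, so the size is unknown and probably small. Under the assumed 5–10% of placebo patients gaining 10–20 points, with none in the active arms, the loss is 0.5–2.0 points of a 30-point difference.

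Three stronger readings are tempting and are not supported:
- *The lack-of-response rule biases the Week 16 result.* It cannot act before Week 28. It touches only later data, such as the Week 52 secondary endpoint, where the 6-week cut-off limits it.
- *The planning assumptions show how many placebo patients are affected.* One could compute the share at Week 16 who are neither clearly improved nor worse. That share counts nobody to whom the rule applies, and it says nothing about how many take other treatment.
- *NRI would turn such a patient into a responder.* NRI fills missing visits only. A value that EC keeps is used as observed.

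**What to change.** 1. **Protocol 3.3.4.1 and 4.2.2.1:** reconcile when a treatment is called rescue. The clinical rule, including any effect on trial treatment, is the sponsor's decision.
2. **SAP 5.1, 5.2.2 and 6.3:** state one trigger for EC and NRI, for example: *Any treatment of a type listed under rescue therapy in CTP 4.2.2.1 that is given for PPP, whatever the stated reason, is handled as rescue therapy for censoring.* This governs data handling only.
3. **Protocol 7 and 7.3, SAP 6.6.2, and codes D2.01a/b and D2.02a/b:** align with that sentence.
4. **EC-EP:** list the therapies it covers, including whether tonsillectomy is among them, since Table 4.2.2.1: 1 is headed as pre-randomisation and omits it.
5. **CRF:** confirm that it records the indication. The trigger still needs to separate treatment for PPP from treatment for another condition. The documents mention time of intake and dose (Protocol 4.2.2.1) and start date and changes (Protocol 8.3.1), but not indication.

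The cost is a protocol clarification, a few lines of SAP text and a few more censored values, which the MMRM handles as missing at random. EC and EC-EP would then differ only in treatments not given for PPP, which makes EC-EP easier to interpret.
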